### Study Assessments

1. At baseline, we will record each subject's chief complaint, age of onset of mood and/or cognitive decline, number prior depressive episodes, age, sex, marital status, race and ethnicity, years of education, employment status and income, years of education, and family history. Medical history will be documented, and physical exam, urine drug screen, CBC, chemistries and electrolytes, thyroid profile, vitamin B12 and folate levels, urine analysis, and ECG will be performed. Vital signs will be measured at baseline and monitored throughout the study. The Cumulative Illness Rating Scale-Geriatric (CIRS-G) (81) will be filled out at baseline to measure chronic medical illness burden. Psychiatric diagnosis and eligibility will be determined at screening using the Structured Clinical Interview Diagnostic for DSM 5 (SCID) (82), 24-item HRSD and MMSE.

2. As described below, patients will return for follow up audiology visits at the Columbia Otology and Neuro-otology Clinical Practice at Weeks 0, 2, 6, and 12. At Week 6, if the hearing aid devices are functioning well and the patient is meeting the usage requirement, the audiologist will ask if the patient would like to skip the Week 9 audiology visit and return at Week 12. However, if the patient's hearing aid use does not meet the requirement at Weeks 2 and/or 6 (as determined by the data log) or if there are any hearing aid complications, they will be scheduled for an audiology visit at Week 9. Patients will visit the Clinic for Aging, Anxiety, and Mood Disorders for psychiatric follow up visits at Weeks 0, 2, 4, 6, 9, and

12. However, a weekly CGI severity score of 6 or 7 will prompt a weekly session to check-in with the patient.

3. At psychiatric follow up visits patients will complete the 24-item HRSD, CGI Severity and Improvement, Structured Pill Count Interview (assessment of study medication compliance), Treatment Emergent Side Effect Scale (standardized general checklist used in our clinic for monitoring side effects), Inventory of Depressive Symptoms—Self Report (IDS-SR), Social Adjustment Scale, and Blind assessment—Clinician and Patient Versions (rates clinician and participant’s guess as to the identity of full vs. low amplification hearing aids). Medical interns who come to our clinic for 4-week rotations and psychiatry fellows who come to our clinic for 6-month rotations during the Spring semester, may complete psychological assessments on study participants. All medical interns and fellows will have completed NYSPI-specific CITI training for humans subjects research (specifically the biomed or social/behavioral course).

4. At baseline and study endpoint, participants will undergo neuropsychological evaluation. The neuropsych battery will comprise the Repeatable Battery for the Assessment of Neuropsychological Status (RBANS) (78-79), which was designed to reliably examine intelligence, attention, memory, language, and visuospatial/constructional ability (80-81). Because the RBANS requires instructions and some stimuli to be presented auditorily to each participants, Claes and colleagues (2016) adapted the battery for specific use in hearing impaired populations (82). This RBANS for Hearing Impaired Populations (RBANS-H) will be employed in the current study, and all components of the RBANS-H the instructions in are presented in written format on an external computer monitor simultaneous with the oral administration. Because the RBANS-H has relatively low coverage of executive functioning, we are supplementing it with measures from the NIH Toolbox (Dimensional Change Card Sort Test and the Flanker Inhibitory Control and Attention Test) (83).

5. At baseline and study endpoint, participants also will undergo functional evaluation. Domains of function assessed include: the Short Physical Performance Battery (SPPB) (94), a performance measure of gait, balance, and lower extremity strength sensitive to meaningful change. Patients’ gait will be assessed by trained raters as walking speed in m/s on a Gaitrite walkway system. Patients are instructed to walk at their usual or normal speed starting and ending at a point 6 feet prior to and after the walkway course to eliminate acceleration and deceleration effects. Two trials will be completed, and gait speed will be based on the average of 2 trials. Physical activity is assessed via a measure of weekly kilocalories (kcal) derived from the 18-item Minnesota Leisure Time Physical Activity Questionnaire (106), with activity levels < 383 kcal considered frail. The 36-item self-report World Health Organization Disability Assessment Schedule 2.0 (WHODAS2) provides a global measure of disability and 7 domain-specific scores based on the conceptual framework of the International Classification of Functioning, Disability, and Health (ICF) (95). The self-report 38-item Measure of Everyday Cognition (ECog) is adapted from an informant-report version and measures impairment and change in domains of everyday/real-world functioning relevant to 7 specific neuropsychological domains (96).

#### Hearing aid procedures

1. For audiological assessment, the patient will be seated in a double walled soundproof booth. Pure tone testing will be performed using insert earphones and bone conducted stimuli. Frequencies tested include 250 Hz, 500 Hz, 1k Hz, 2k Hz, 3k Hz, 4k Hz, 6k Hz and 8 k Hz. Speech reception thresholds (SRT) will be

obtained in each ear using standard spondee words. Word recognition will be assessed in each ear using a recorded CNC (consonant-vowel nucleus-consonant) type word list (25 words) at 40dB SL above the patient's SRT. Screening: subjects will have testing of pure tone thresholds, SRT, and word recognition as above.

2. At Week 0, The Hearing Handicap Inventory for the Elderly (HHIE) (77) will be administered, which is a 10-item questionnaire developed to assess how an individual perceives the social and emotional effects of hearing loss. Unaided word recognition will be tested using CNC at 50dB HL and AzBio sentences (condition 1: signal 50dB HL in quiet, condition 2: signal 50dB HL with a +5 SNR using 4 talker babble), both presented at 0° azimuth.

3. Hearing aids will be the latest Audeo B-R 90 devices manufactured by Phonak. Low amplification and full amplification hearing aids will be identical in appearance, battery use, and data logging capability. Low amplification hearing aids will be programmed to prescription for a flat 30dB hearing loss, which will result in a small but noticeable volume increase without substantively improving subject's ability to discriminate speech, which we believe is important for the hearing aids' effect on depressive symptoms. Full amplification hearing aids will have their gain determined by audiometric profile as per standard clinical practice. Real ear measures will be performed to verify fitting, education and counseling will be provided regarding the use of the hearing aid, and subjects will be informed that a minimum of 8 hours/day hearing aid usage is required to stay in the study. To assess compliance with hearing aids, we will measure usage rates (hours/day) using data log technology built into the hearing aids (69-70) Subjects will also sign a hearing aid agreement which includes the provision that if the subject does not complete the 12-week study they must return both hearing aids. If the subject does not complete the 12-week study and would like to keep the hearing aids, he/she can buy the hearing aids at market cost (\$5,300). If a subject does not return the hearing aid, he/she will be charged at market cost for the hearing aid (\$5,300) to the CUMC/Audiology Department. Furthermore, if the subject does not wear the hearing aids for at least 8 hours a day this will disqualify him/her from the study and he/she will have to return all devices. However, if during the study period the subject breaks or loses the hearing aids, we will provide them a new device at no cost to the subject. .

4. Subjects will have follow up audiology appointments at Weeks 2, 6, and 12, during which their questions about hearing aid usage will be answered and the data log will be checked and reset. At Week 6, if the hearing aid devices are functioning well and the patient is meeting the usage requirement, the audiologist will ask if the patient would like to skip the Week 9 audiology visit and return at Week 12. However, if the patient's hearing aid use does not meet the requirement at Weeks 2 and/or 6 (as determined by the data log) or if there are any hearing aid complications, they will be scheduled for an audiology visit at Week 9. At Week 12, endpoint measures will be collected, which comprise the HHIE and repeat of audiological measurements from Week 0.

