### Overview

Following baseline evaluation and MRI scanning, each subject will be counseled on the role of antidepressant medications in clinically significant depressive disorders as well as the risks and benefits of starting/changing antidepressant medication. Subjects will be randomized to receive antidepressant medication (AD) in combination with either full amplification hearing aids or low amplification hearing aids. Subjects who do not wish to change their antidepressant medication will also be offered participation in a subgroup of the study and will be randomized to receive either full amplification hearing aids or low amplification hearing aids. Subjects, treating clinicians, and depressive/cognitive outcome assessors will be blinded to hearing aid assignment. At randomization (Week 0) subjects will have devices placed and receive education by an audiologist, who will not be blinded but will conduct identical procedures for full vs. low amplification hearing aids and will maintain the blinding with participants. Subjects will have follow up audiology appointments at Weeks 2, 6, and 12 to receive further education, monitor compliance, and ensure devices are working correctly. Failure to adhere to hearing aid use requirements at Weeks 2 and/or 6 (as determined by the usage data log), or any hearing aid complications will prompt an additional audiology appointment at Week 9. At Weeks 2, 4, 6, 9, and 12 subjects will complete depression follow-up visits. However, a weekly CGI severity score of 6 or 7 will prompt a weekly session to check-in with the subject.

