## Criteria for Early Discontinuation

### Criteria for Early Discontinuation

The risk of receiving low amplification hearing aids, no antidepressant medication, or non-response to antidepressant medication during the study period is addressed by having close clinical follow up of study subjects and stringent withdrawal criteria. These criteria are (1) participant withdraws his or her consent; (2) significant clinical worsening in the judgment of the study clinician; (3) a CGI-Improvement rating of 6 (worse) or 7 (much worse) for 2 consecutive visits; or (4) development of significant side effects or an adverse event. Any subjects meeting any of these criteria will be withdrawn from the study and treated

clinically. Furthermore, subjects may be withdrawn if they repeatedly miss scheduled appointments or clinical worsening necessitates more intensive treatment.

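### Hearing-aid use under 8 hours a day disqualifies a randomised participant, other sections keep that participant in, and nothing secures the Week 12 data

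*Protocol*

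**What the plan says.** **The rule.** Protocol, Hearing aid procedures, item 3, tells participants that "a minimum of 8 hours/day hearing aid usage is required to stay in the study". It then states that "if the subject does not wear the hearing aids for at least 8 hours a day this will disqualify him/her from the study", with all devices handed back. It gives no averaging period, decision visit or decision-maker. The same item provides that "if the subject does not complete the 12-week study they must return both hearing aids".

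**Timing and arms.** The Overview states: "At randomization (Week 0) subjects will have devices placed". Item 3 describes the low-amplification setting as giving "a small but noticeable volume increase without substantively improving subject's ability to discriminate speech".

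**A different consequence for the same failure.** In the Overview, failing the use requirement on the data log at Week 2 and/or 6 "will prompt an additional audiology appointment at Week 9". Study Assessments item 2 and Hearing aid procedures item 4 say the same. Item 4 adds that the log is read and reset at audiology visits.

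**Withdrawal criteria.** Criteria for Early Discontinuation begins: "These criteria are (1) participant withdraws his or her consent; (2) significant clinical worsening in the judgment of the study clinician". It goes on to two consecutive poor CGI-Improvement ratings and to side effects or adverse events. It then adds that "subjects may be withdrawn if they repeatedly miss scheduled appointments or clinical worsening necessitates more intensive treatment". Low use does not appear.

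**Analysis.** SAP, Data Analysis, uses ANCOVA on change from Week 0 to Week 12, describes the model as covering all participants, and gives no missing-data method. It also compares hours of use between arms at Weeks 2, 6 and 12. Description of Subject Population sets 40 enrolled and 32 completers. Specific Aims includes an exploratory aim on how logged compliance relates to change in symptoms and executive function.

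**The concern.** The rule acts after randomisation, on a behaviour that the assigned device may affect: someone who gains little speech discrimination has less reason to wear the aids all day. No section provides a Week 12 assessment for a disqualified person. A model said to cover all participants cannot use a value that was never collected. If the rule is enforced, the depression and cognition contrasts compare those who wore the aids enough, not those who were randomised.

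The text also does not settle who is analysed. One item ends participation, three places schedule a further visit, and the withdrawal list is silent. Two staff members could treat the same log differently.

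Three things are at stake:

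- the validity of the between-arm contrasts;
- the number of completers;
- the exploratory compliance aim, which would lose the Week 12 change of the low users it most needs.

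**Working it through.** **1. The plan's own figure.** 1 − 32/40 = 20% implied attrition, and 32/(1 − 0.20) = 40, so enrolment and completers agree. The allowance is 40 − 32 = 8 losses from all causes. No alpha, power, effect size or SD is stated, so the planned power cannot be reproduced.

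**2. The sections side by side, for use under 8 h/day**

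| Place in Protocol | Consequence |
|---|---|
| Hearing aid procedures, item 3 (twice) | Leaves the study; devices returned |
| Overview; Study Assessments item 2; Hearing aid procedures item 4 | Week 9 audiology visit; stays in |
| Criteria for Early Discontinuation | Not listed |
| Any section, Week 12 follow-up of a disqualified person | None |

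The log resets imply check times and visit-to-visit windows, but nothing links them to disqualification. The discontinuation list addresses clinical risk, so its silence does not clearly cancel item 3.

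**3. Shift in the HRSD contrast.** The documents give no usage or outcome figures, so every input here is assumed. If the share p with lowest use is removed from an arm, and use correlates ρ with improvement, the retained mean improvement shifts by ρ × SD × φ(z_p)/(1 − p), where z_p is the normal quantile at p. Bias is the full-arm shift minus the low-arm shift, so a positive value favours full amplification. SD = 8.

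| Removed, full v low | ρ, full v low | Shifts | Bias (points) |
|---|---|---|---|
| 20% v 20% | 0.4 v 0.4 | 1.12 − 1.12 | 0 |
| 15% v 35% | 0.4 v 0.4 | 0.88 − 1.82 | −0.95 |
| 15% v 35% | 0.4 v 0 | 0.88 − 0 | +0.88 |
| 20% v 20% | 0.4 v 0 | 1.12 − 0 | +1.12 |
| 10% v 40% (extreme) | 0.5 v 0.5 | 0.78 − 2.58 | −1.80 |

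The unadjusted standard error with 16 per arm is 8 × √(2/16) = 2.83. The extreme case is 1.80/2.83 = 0.63 SE; the others are at most 1.12/2.83 = 0.40 SE. Equal removal does not guarantee zero bias: the fourth row differs from the first only in ρ.

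**4. Usage ANOVA.** Hours logged up to a failed check are already recorded, so only later time points are affected. Assume SD 3 h, removal when true use is below 8 h, and equal weight for the three visits. Retained means follow from the normal distribution truncated at 8 h:

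- mean 12: 9% below 8 h, retained mean 12.54;
- mean 10: 25% below, retained mean 11.28;
- mean 9: 37% below, retained mean 10.80.

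| True means (h/day) | True difference | Retained difference | Visit average, only Week 12 affected | Visit average, Weeks 6 and 12 affected |
|---|---|---|---|---|
| 12 v 10 | 2.0 | 1.26 | (2.0 + 2.0 + 1.26)/3 = 1.75 | (2.0 + 1.26 + 1.26)/3 = 1.51 |
| 10 v 9 | 1.0 | 0.49 | (1.0 + 1.0 + 0.49)/3 = 0.83 | (1.0 + 0.49 + 0.49)/3 = 0.66 |

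The retained difference is what the Week 12 cell alone would show if each person's use were perfectly stable. If use at removal and at Week 12 correlate 0.7, that cell shows 1.48 h and 0.64 h.

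**5. Completers.** With an assumed 10% other dropout, 36 remain (18 per arm), so the rule can remove 36 − 32 = 4 people (4/36 = 11%) before the count falls below 32.

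| Removed, full v low | With 10% other dropout | With no other dropout |
|---|---|---|
| 10% v 20% | 36 − 18 × 0.30 = 30.6 | 40 − 20 × 0.30 = 34 |
| 15% v 40% | 36 − 18 × 0.55 = 26.1 | 40 − 20 × 0.55 = 29 |

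**The case against.** The strongest reply is that the sections can be read in sequence: counsel at the failed check, bring the participant back at Week 9, and disqualify only for persistent low use. On that reading item 3 is a term of the hearing aid agreement that backs up compliance. Even a Week 2 failure then carries the person to Week 9. This is plausible, but it is written nowhere, item 3 is unconditional, and persistent low users would still be removed before Week 12.

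Several further points are fair:

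- Nothing shows that anyone was disqualified, and the bias argument depends on enforcement.
- Outside the extreme case the shift is at most 0.4 SE. In that case 18 and 12 remain, so the standard error is 8 × √(1/18 + 1/12) = 2.98 and the ratio 0.60.
- Low users and other dropouts may overlap, and the allowance of 8 may already include usage removals. Either would lessen the completer shortfall.
- The missing-data gap affects all dropout, and the SAP specifies no use–outcome analysis for the compliance aim.
- A minimum-wear requirement is a defensible choice in a trial whose rationale criticises earlier studies for lacking objective use data. But requiring and supporting wear does not require outcome collection to stop for those who fall short.
- The SAP is in the past tense, so rewording the Protocol may come too late to change who was kept. The reporting items remain useful.

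**Conclusion.** The concern holds. Item 3 makes low use after randomisation a ground for leaving the study, other sections prescribe continuation for the same failure, and no section secures the Week 12 value that the SAP needs. Applying item 3 at any stage before Week 12 selects the randomised comparison on post-randomisation behaviour. If staff followed the Week 9 route throughout, low users stayed and this selection does not arise.

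The size is modest and the sign is open: 0 to about 0.6 SE on HRSD, and zero if removal is equal between arms and relates equally to outcome. The usage comparison would be understated in the scenarios tried. Completers could fall to 26–31 with 10% other dropout, or 29–34 with none. All usage, correlation, SD and dropout inputs are assumptions. The conflict between sections and the missing Week 12 provision rest on the text alone. The point should be fixed; confidence in its practical effect is medium.

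**What to change.** - **Hearing aid procedures, item 3:** replace disqualification with a device-adherence rule. Define it as mean logged hours per day since the last reset, read at Weeks 2 and 6, with the existing Week 9 audiology visit as the consequence.
- **Item 3 and Criteria for Early Discontinuation:** state that low use is not a reason for withdrawal. Every randomised participant stays in scheduled assessments through Week 12 unless consent is withdrawn, and is analysed in the assigned arm.
- **Incentive:** keep the existing link between completing the 12 weeks and keeping the aids.
- **SAP, Data Analysis:** report the number below 8 h/day by arm. Since the SAP is in the past tense, if anyone was disqualified also report how many by arm, when, and whether Week 12 data were collected.

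The cost is wording in two Protocol sections, the consent form and the hearing-aid agreement, plus one or two SAP lines. The visits are already scheduled, and under the COVID-19 re-opening procedures the psychiatric follow-up is largely virtual. The downsides are slight dilution from including low users and a weaker 8-hour incentive. The Week 12 neuropsychological, physical and audiology measures and the endpoint MRI still need attendance in person, so some low users may not provide them.

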#### Antidepressant medication

1. Following baseline screening, subjects who choose to start a study medication will receive escitalopram 10mg per day or duloxetine 30mg per day. We opted to allow two potential medication choices so that study participation could be offered to individuals who had previously taken one medication and either not responded or not tolerated it. We selected escitalopram and duloxetine based on established efficacy in

MDD, favorable side effect profiles, minimal drug-drug interactions, and cost effectiveness (i.e., available as generics) (67-68).

2. If the best history-taking efforts of study staff (including patient interview, pharmacy records, or other medical records) indicate that a participant has not responded to or has not tolerated escitalopram or duloxetine, then we will offer an alternative SSRI, SNRI, or bupropion based upon our clinical assessment of the best option given the participant's other medications, medical health, and symptom profile. Similarly, if the patient either fails or is unable to tolerate both of the study medications during the study, they will be initiated on another medication that is clinically indicated. If this is the case, the subject receiving non-study AD medication will be responsible for the cost of the medication co-pay and will pick up the prescriptions from their pharmacy.

3. After 4 weeks if subjects do not meet remission criteria ( $HRSD \leq 10$ ), the dose of study medication will be increased to escitalopram 20mg or duloxetine 60mg for the remaining 8 weeks of the study. Similarly, the dose of the non-study antidepressant medication will be increased under the guidance of the study clinician. Subjects unable to tolerate an increased dose will have their medication reduced to the previously tolerated dose. If a study subject wishes to change antidepressant medication at any point during the study period they may do so under the guidance of the study clinician.

#### MRI procedures

1. Participants will undergo an MRI scan at baseline and study endpoint (prior to unblinding).

2. Image Acquisition: MRI of the brain will be conducted using the following sequences: (1) Axial IR-FSPGR TE/TR=3ms/6.5ms, TI=450ms, flip angle=12°, voxel size=1x1x1mm, 180 contiguous slices, total acquisition time=4min; (2) Multi-Band (or Simultaneous Multi-Slice) EPI, TE/TR=30/800ms, flip angle=52°, matrix=90x90, voxel size=2.4x2.4x2.4mm, acquisition time=5min(rs-fMRI)/7min(task-fMRI); (3) for DWI, TE/TR=88ms/4100ms, voxel size=1.7x1.7x1.7mm, flip angle=90°, FOV=240x240 mm, matrix=140x140, diffusion directions=102, b value=1000s/m^2, acquisition time=7.5min, (4) 3D T2-weighted FLAIR, TE/TR=144/8000ms, voxel size=1x1x1mm, acquisition time=8 min. During the fMRI scanning, subjects' wakefulness will be monitored using a MR-compatible eye-tracking camera.

3. Simon Task: For the Simon Task, a series of white arrows pointing either left or right is displayed against a black background either to the left or right of a white gaze fixation cross-hair positioned at midline. Stimuli are 'congruent' (arrows pointing in the same direction as their position on the screen) and 'incongruent' (pointing in a direction opposite their position on the screen). Each experiment contains 3 runs, totaling 66 incongruent and 66 congruent stimuli. Participants are instructed to respond as quickly as possible to the direction of the arrow by pressing one of 2 buttons on a response box. Stimulus duration is 1300ms, with jittered inter-stimulus intervals ranging from 4 to 7 seconds. Behavioral outcome measures are reaction times (RT) and accuracy scores on congruent and incongruent trials, and the Simon effect (mean RT incongruent > mean RT congruent).

4. Subject Comfort: For the MRI procedures, the subject will be instructed to lie as still as possible within the magnet for approximately 30 minutes. When we position a subject in the scanner, head movement will be minimized through: (a) instructions to the participant; and (b) packing the head inside the head coil with

a system of foam padding and pillows that we have found is well-tolerated by the participants, yet limits movement. All precautions and protections will be given to the participant to ensure that they are as safe and comfortable as possible. For the participant's comfort within the scanner, they will lie on a padded table with a pillow to rest their heads on. A blanket will also be provided to keep subjects warm during the procedure.

5. Anxious/Nervous Subject: If the participant appears nervous or anxious, a trained member of the clinical staff will remain with them inside the scanning suite for the duration of the scan. The participant will be given a button box to terminate the scan at any time. If they push the button, they will be removed from the scanner immediately.

6. MRI Conduction: All of the MRI procedures will be conducted on the 3-Tesla MRI scanner at the New York State Psychiatric Institute. Conducting these procedures will be an accredited Magnetic Resonance Technologist (B.M.R.) and a member of the research staff (Bachelor's Level or Higher) trained in the acquisition of MR images, as well as in procedures for testing human subjects.

7. MRI Reading: Although our MRI Scans are for research purposes, a radiologist will perform a clinical reading on every MRI within 1 month of scanning; if anything clinically significant is found, [name] will be notified immediately and he will provide an appropriate clinical referral to the participant. We will send the subject one of three MRI result letters reflecting findings of (1) no significant findings (2) findings to be discussed with study physician (3) significant irregularity that necessitates immediate follow-up

8. Safety Precautions: While scanning parameters may change slightly, power monitoring software on the scanner will ensure total energy delivered to the subject will remain within FDA guidelines. Specifically, the specific absorption rate (SAR) will be not greater than: (1) 4 W/kg averaged over the whole body for any period of 15 minutes; (2) 3 W/kg averaged over the head for any period of 10 minutes; (3) 8 W/kg in any gram of tissue in the head or torso; (4) 12 W/kg in any gram of tissue in the extremities, for any period of 5 minutes. These safety precautions are built into the MRI hardware, and are standard with every system.

9. Image processing and analysis: fMRI scans will be preprocessed using SPM 12 (slice-timing correction, motion correction, spatial normalization, and smoothing with 8mm FWHM). Region-of-interest (ROI) and whole brain analysis will be done with False Discovery Rate control (86). Regions within the CCN will constitute our ROI, given an association of decreased connectivity with LLD (87) and antidepressant response (88) (e.g., the DLPFC, dACC, supramarginal gyrus, putamen, and anterior insula) (89). Simon-Task fMRI: Preprocessed data will be entered to a subject-level regression model with 3 regressors (convolved with the canonical hemodynamic response and time derivative) corresponding to 1) congruent correct trials, 2) incongruent correct trials, and 3) incorrect trials. T-contrast images of "incongruent-minus-congruent" in each participant will be entered into a group-level mixed effects model. Resting MRI: Seed-based intrinsic functional connectivity will be carried out in the CONN toolbox v13 (90). Mean BOLD time series of each seed region will be correlated (Pearson's correlation) with timeseries of every other voxel's. Structural MRI: Morphometric measures (volume, thickness, surface area, etc) will be estimated using Freesurfer suite (91). WMH volumes will be estimated from FLAIR image using a semi-automated method by which WMH are seeded and passed through an iterative algorithm to yield WMH volumes. DWI: DWI will be preprocessing in MRtrix3 (92) (brain extraction, PCA-based denoising (93), eddy current correction (94), distortion correction (95), tensor modeling fitting to get anisotropy and diffusivity measures). Two

analyses will be performed: probabilistic tractography within the CCN ROIs (as above, 92), and voxel-based morphometry optimized to WM tracts (Tract-Based Spatial Statistics) (96). For probabilistic tractography, structural connection strength will be indexed by number of estimated WM streamlines (NOS; validated quantification of WM projection strength) (97). Further, quantitative nature of tractography will be enhanced by filtering out non-biologically plausible (false-positive) streamlines using Spherical-deconvolution Informed Filtering of Tractograms (SIFT) (98). For voxel-based morphometry (TBSS), diffusivity (MD) and anisotropy (FA) images will be warped into a study-specific template brain and projected onto alignment-invariant tract representation.

